8.1. Study Device Supply

A designated Sponsor employee independent from the clinical trial will be delegated authority for shipping supplies to enrolled subjects (heretofore referred to as "Shipping Associate"). This individual will not reveal any PHI or PII to the other Sponsor employees involved in the clinical trial.

Once a subject is enrolled, the Shipping Associate will be informed of the type of devices to ship (active device or sham), quantity, and the name and address to ship to. The Shipping Associate will expedite the package to the newly enrolled subject.

If subject has not received devices by the expected delivery date, site staff must contact the Shipping Associate to re-send the package. Shipment and Confirmation Logs will be kept by the sites.

8.2. Study Device Reconciliation and Destruction

Subjects are asked to retain all used and unused study devices throughout the Treatment Period. At the end of the Treatment Period, or otherwise determined by the Sponsor, subjects will be asked to return all used and unused study devices by mailing the devices using supplied shipping materials.

Number of lost, used, and unused devices will be reconciled for each subject.

The Sponsor will retain devices. Device destruction or disposition is at the discretion of the Sponsor.

8.3. Other Study Supplies

Study-related documents, investigator binders, study subject binders, and project trial binders will be provided by the sponsor. Other supplies will be supplied as needed and negotiated by site.

9. SAFETY ASSESSMENTS

9.1. Specification of and Methods for Collecting Safety Parameters

Subjects will be able to report safety concerns on their surveys and Diaries. Subjects may also contact their assigned site staff directly with safety concerns. Subjects will be instructed to report any safety concern or medical event including injury, sickness, hospitalization or other adverse event that occurs during their involvement in the study.

9.2. Adverse Events and Serious Adverse Events

An adverse events (AE) is any unexpected medical problem experienced by the subject that occurs during treatment or during the study that may or may not be associated with the treatment.

A serious adverse event (SAE) is any AE that results in a life-threatening situation, inpatient or prolonged hospitalization, significant incapacity or disruption of normal life functions, abnormal birth defect, or death. Any major medical event that may jeopardize the subject and may require medical or surgical intervention may be interpreted as SAEs.

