3.3. Potential Risks & Benefits

3.3.1. Known Potential Risks

Immediate risks related to the device include skin irritation or reaction to the adhesive used on the device, and discomfort related to any forces that the device applies to the wrist.

Previous studies have found the study device can be worn for over 12 hours with little to no discomfort and minor to no redness.⁹

The sham device is the same as the active device but with a cushion on the underside. This cushion is similar to sponges used for make-up or healthcare applications.

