9.3. Reporting Procedures

Site staff and Sponsor's Clinical Research Manager will regularly monitor survey and Diary responses (e.g., daily for Diaries and as they come in for other surveys) for any safety concerns. Severity and relatedness of patient-reported safety concerns will be assessed by the PI or appropriately qualified site staff member. If determined to be the level of an adverse event or serious adverse event, the safety concern will be recorded in the AE/SAE Log within the IRB's reporting timeframe. The PI or appropriately qualified site staff member will determine the necessary follow-up medical response.

Minor AEs such as minor injuries (e.g., sprains, cuts, bruises) or minor illnesses (e.g., colds, flus, food poisoning) that are clearly not associated with device do not need to be reported to the Sponsor or IRB. AEs that result in injury to the affected wrist area or in discontinuation of device use should be reported to the Sponsor.

SAEs are to be recorded as soon as possible from the discovery of the SAE and both the PI, sponsor, and IRB notified promptly. The Sponsor should notify all sites of an SAE. AEs/SAEs should be reported within the timeframes from IRB and GCP guidelines.

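### The adverse event definition in 9.2 is limited to unexpected problems, so the device risks listed in 3.3.1 need not be logged, followed up or counted as AEs

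*Combined protocol and SAP*

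**What the plan says.** The relevant text is in five places in the combined protocol and SAP.

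- **9.2, AE definition.** An AE is "any unexpected medical problem experienced by the subject". The definition spans the whole study and adds a clause on relatedness: "that may or may not be associated with the treatment".
- **9.2, SAE definition.** The first sentence builds on the AE definition: "A serious adverse event (SAE) is any AE that results in" one of a list of serious outcomes. A second sentence allows a major medical event that endangers the subject and may need intervention to be interpreted as an SAE.
- **3.3.1, Known Potential Risks.** The text there reads: "Immediate risks related to the device include skin irritation or reaction to the adhesive used on the device, and discomfort related to any forces". The forces meant are those exerted by the device on the wrist.
- **9.1, 9.3 and 9.4, from report to log to follow-up.** Subject reporting is broad: "Subjects will be instructed to report any safety concern or medical event including injury, sickness, hospitalization or other adverse event". Entry in the log is narrower: "If determined to be the level of an adverse event or serious adverse event, the safety concern will be recorded in the AE/SAE Log". Under 9.4, repeated contact at later follow-ups is required for AEs that have been reported and recorded.
- **10.5, safety analysis.** This gives the population (all subjects who received treatment). It gives no safety endpoint, event list or tabulation.

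**The concern.** Expectedness is normally an attribute of an event, used to decide how urgently it is reported. Here it is part of the test for whether an event is an AE at all. A risk the protocol has already listed is, in the ordinary sense, expected. The definition can therefore exclude the reactions most plausibly caused by the device, while an unrelated surprise illness qualifies.

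The trial is labelled confirmatory/pivotal in the synopsis (2.1), and earlier experience is thin. The pilot had 13 subjects (10.2) and 4 weeks of treatment, against 8 weeks here (5.2). Section 5.2 also reports occasional comments about discomfort from the device edges and a redesign to reduce uncomfortable pressure points. How often the redesigned device irritates or hurts the wrist is a question this trial should answer, and an AE table built on 9.2 might not answer it.

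**Working it through.** No arithmetic applies. The point depends on no significance level, power, effect size or sample size, and the documents give no event rates. The check follows one event, an adhesive rash reported in a Diary, through the stated rules.

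1. **Is it reported?** Yes. Section 9.1 asks subjects to report any concern, and 9.3 has site staff and the Sponsor's Clinical Research Manager review Diaries daily and surveys as they arrive.
2. **Is it expected?** In the ordinary sense, yes. Section 3.3.1 lists it under known risks: "Immediate risks related to the device include skin irritation or reaction to the adhesive used on the device".
3. **Is it an AE under 9.2?** Read literally, no. The clause on association with treatment widens the definition on relatedness only; it does not cancel the requirement that the problem be unexpected. The protocol does not define that word or say that it carries some other meaning.
4. **Is it entered in the AE/SAE Log?** Section 9.3 requires this only if the concern is judged to be an AE or SAE. If step 3 gives no, no rule requires entry.
5. **Is it followed up?** The repeated contacts in 9.4 attach to recorded AEs. If step 4 gives no, they are not required.
6. **Is it counted?** Section 10.5 does not ask for anticipated device effects to be tabulated separately. An event absent from the log would be counted only if someone chose to retrieve it from the survey or Diary data.

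The same chain applies to discomfort from device forces. All the immediate device risks named in 3.3.1 are therefore affected.

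**Consistency between sites.** A site that takes the word literally stops at step 3. A site that reads it as *untoward* logs the rash and follows it. Both comply with the text. With at least three sites (2.1), the recorded rate could depend partly on which reading each site adopts.

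**Serious events.** The first SAE sentence inherits the AE limit. The second does not refer to AEs or to expectedness, so a major event can still be classified as an SAE. That route is permissive rather than mandatory.

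**The case against.** The strongest reply is that the sections, read together, show an intention to capture device effects. Section 9.3 has the site assess severity and relatedness and does not list expectedness as a test. Its exemption for minor AEs covers only events clearly unrelated to the device, and only as to reporting to the Sponsor or IRB. AEs that injure the wrist or stop device use go to the Sponsor. Raw data are plentiful: daily Diaries, two-weekly surveys during treatment, and a User Feedback Survey that covers comfort.

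Much of this stands. The reports will exist, and the authors probably did not mean to exclude device reactions. But the 9.3 rules on exemption and Sponsor reporting apply to events already classed as AEs, so they do not repair the definition. If the intention was to capture these effects, the wording works against it.

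Three stronger readings are tempting, and the documents do not support them.

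- *Expected device effects are systematically excluded.* The wording permits omission; it does not order it, and some sites may log these events anyway.
- *A serious expected event cannot be an SAE.* The second SAE sentence leaves a route open. A reaction far more severe than the minor ones described in 3.3.1 could also be called unexpected in its severity.
- *The active-versus-sham safety comparison is biased toward no harm.* No such comparison is specified in 10.5. The sham is described as the same device with a cushion, so under-logging could occur in both arms. If the same share of events went unlogged in each arm, an absolute difference would shrink, but that equal share is an assumption, and the documents do not show what would happen to the difference.

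**Conclusion.** The point holds as a defect in AE classification, logging, follow-up and tabulation. Under the plain wording of 9.2 and 9.3, the only immediate device risks the protocol names need not appear in the AE log, and sites may treat the same reaction differently. Recorded AE rates for these effects could be understated. The size cannot be given, because the documents contain no rates for irritation, adhesive reaction or discomfort.

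This rests on two assumptions: that a risk listed in 3.3.1 counts as expected, and that at least some sites apply the word as written. It is not a loss of all safety data, and no bias in a between-arm comparison has been shown. The efficacy analyses and the sample size are unaffected. The change should be made because the affected events are the ones of most interest for this device and the correction is small.

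**What to change.** - **9.2:** delete *unexpected*, so that an AE is any untoward medical occurrence during the study, whether or not it is expected and whether or not it is related to the device. The first SAE sentence is then corrected without further editing.
- **9.3:** record expectedness as a separate attribute of each event, beside severity and relatedness. State that the risks listed in 3.3.1 are entered in the AE log when they occur; follow-up under 9.4 then applies to them.
- **10.5:** state that these anticipated device effects are tabulated by group in the safety analysis.

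The cost is a few sentences and slightly more AE log entries, drawn from reports that 9.1 and 9.3 already have collected and reviewed. No sample size or power figure changes.

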9.3. Reporting Procedures

Site staff and Sponsor's Clinical Research Manager will regularly monitor survey and Diary responses (e.g., daily for Diaries and as they come in for other surveys) for any safety concerns. Severity and relatedness of patient-reported safety concerns will be assessed by the PI or appropriately qualified site staff member. If determined to be the level of an adverse event or serious adverse event, the safety concern will be recorded in the AE/SAE Log within the IRB's reporting timeframe. The PI or appropriately qualified site staff member will determine the necessary follow-up medical response.

Minor AEs such as minor injuries (e.g., sprains, cuts, bruises) or minor illnesses (e.g., colds, flus, food poisoning) that are clearly not associated with device do not need to be reported to the Sponsor or IRB. AEs that result in injury to the affected wrist area or in discontinuation of device use should be reported to the Sponsor.

SAEs are to be recorded as soon as possible from the discovery of the SAE and both the PI, sponsor, and IRB notified promptly. The Sponsor should notify all sites of an SAE. AEs/SAEs should be reported within the timeframes from IRB and GCP guidelines.

9.4. Follow-up for Adverse Events

Site staff should contact subjects that report an AE within 3 days of learning of the AE, unless the AE is minor (see above).

For subjects with a reported and recorded AE, site staff should contact the subject at each subsequent Follow-up (i.e., every 2 weeks during Treatment Period, every 4 weeks during Post-Treatment Period) to obtain an update on the status of the AE/SAE. The AEs should be followed until resolved, considered stable, or the subject is exited from the study.

10. STATISTICAL CONSIDERATIONS

10.1. Statistical Hypotheses

10.1.1. Primary Efficacy Endpoint

H₀: Daily wear of the study device does not improve symptom severity.

H₁: Daily wear of the study device improves symptom severity by at least 0.4 points.

10.1.2. Secondary Efficacy Endpoint

H₀: Daily wear of the study device does not improve symptom severity in comparison to sham treatment.

H₁: Daily wear of the study device improves symptom severity by at least 0.4 points more than the sham group.

H₀: Changes in symptom severity are not sustained after stopping treatment.

H₁: Changes in symptom severity are sustained or continue after stopping treatment.

10.2. Sample Size Determination

A total of 102 subjects are required for this study, with 51 in each group.

The outcome measure used for calculations in the SSS of the BCTQ, which ranges from 1 to 5 with 1 being no symptoms (improved) and 5 being the worst symptoms (worsened).

A moderate effect size of 0.4 was chosen, assuming that study device efficacy is 0.4 greater than sham.

The pilot study experienced a drop-out rate of 20% (2 out of 13 total). With the longer treatment and follow-up times of this study, a higher drop-out is expected. Therefore the sample size calculation is modified by an estimated attrition rate of 25%.

The primary objective examines the 8 week vs baseline within-active group SSS change. Sample size determination explanation. The power analysis using the above results in a significance level of 0.05 and a power of 0.94*.

The secondary objective examines the change in SSS after 8 weeks between the active study device and sham groups. Sample size calculation is based on a parallel, one-sided t-test power analysis to identify an effect size of 0.4, standard deviation of 0.7 (based on the pilot study PPS-CTMD-15-001), significance level of 0.05, power of 0.8, and an estimated attrition rate of 25%.

The sample size was chosen to meet both the primary and secondary objectives.

10.3. Randomization and Blinding Procedures

A simple randomization scheme is used to allocate subjects into the treatment group or the sham group. Site staff will be blinded to the randomization list and the Sponsor clinical research team blind to the allocation of each subject.

Blinding will be broken for each sham group participant at his/her first post-treatment follow-up (Week 12) so that the site can offer the sham group participant the opportunity to try the active study device. Complete blinding will be broken at the end of the study when all data has been entered and validated and the database has been locked.

Blinding may be broken if a subject experiences a SAE and if knowledge of the device is necessary for proper medical treatment of the SAE. Due to the low risk and minimal side effects associated with the device from previous studies, unblinding in most cases is not deemed necessary for medical treatment.

The subject's assigned site must obtain approval from the Sponsor to break the blind. After approval, the Shipping Associate responsible for randomization will provide the assignment for the subject in question. After a subject's treatment has been revealed, this must be noted along with reasons for breaking the blind in the subject's records and in the Deviation/Violation Log.

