3.3.2. Known Potential Benefits

Prolonged wear (anywhere from 1 week to 4 weeks) of the study device may reduce symptoms of CTS.⁹

The sham device may cause a placebo effect and reduce symptoms of CTS as well.

4. Objectives & Endpoints

Objective	Endpoints	Explanation
Primary		
Investigate whether daily wear of the study device significantly reduces patient-reported CTS symptom severity.	Symptom Severity Score (SSS) of the Boston Carpal Tunnel Questionnaire (BCTQ) in the treatment group at 8 weeks compared to Baseline.	The SSS is a validated combined measure of the patient's perception of the level and frequency of pain, numbness, tingling caused by CTS. 8 weeks is the end of the treatment period.
Secondary		
Determine whether there is a difference between the active device group and sham group.	Comparing SSS at 8 weeks and between the active device group and sham group.	Between group comparison conducted for the primary outcome variable at the primary endpoint (8 weeks).

Additionally, we will determine if this difference continues post-treatment.	Comparing SSS 1 month post-treatment (12 weeks) between the active device group and sham group.	Single timepoint at 12 weeks compared between groups for post-treatment analysis.
Exploratory		
Does CTS symptom improvement occur before 8 weeks?	Significant reduction in SSS compared to Baseline at any time point before 8 weeks.	Identification of significant SSS reduction before 8 weeks suggests a shorter minimum duration of wear.
Do unilateral and bilateral CTS patients respond differently to treatment?	Change in SSS at 4 and 8 weeks in a unilateral subgroup compared to a bilateral subgroup.	Unilateral patients showed significant SSS improvement in the pilot study, whereas bilateral patients seemed to show none. ⁹ Both 4- and 8-week timepoints compared in case a difference is seen before the end of treatment.
Do patients respond differently based on Baseline severity?	Change in SSS at 4 and 8 weeks in mild, moderate, and severe subgroups.	AANEM guidelines categorize CTS into 3 severity groups.
Describe the effect of study device treatment on patients with hormonal-induced CTS, such as pregnancy.	Change in SSS at or within 8 weeks in a subgroup of pregnant women.	The study device is hypothesized to work primarily for repetitive stress induced CTS. Pregnant women often develop CTS due to swelling of the tissue.

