7.2.4. Randomization

There are two treatment groups: active study device or sham device. Subjects will be equally randomized across all sites to ensure equal and equivalent active device and

sham groups. Randomization will occur using a Sponsor-supplied randomization tool or using the randomization module of the Electronic Data Capture (EDC) platform.

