10.5. Statistical Analyses

The primary efficacy endpoint is the improvement (reduction) in SSS of the treatment group at 8 weeks after the first day of device wear. The primary efficacy endpoint will be analyzed using a paired, one-sided t-test.

The secondary efficacy endpoint is the improvement (reduction) in SSS of the treatment group compared to the sham group at T4 (8 weeks after the first day of device wear). The secondary endpoint will be analyzed using a two sample one-sided t-test.

A repeated measures analysis of variance will be used to evaluate changes over time in both the active and sham groups.

The exploratory endpoints will be analyzed using descriptive methods.

Safety analyses will be performed on all subjects that received treatment.

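### Sections 7.2.4 and 10.2 treat equal arms as assured, but the simple randomisation named in 10.3 gives equality only on average (low severity)

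*Combined protocol and SAP*

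**What the plan says.** Three sections bear on allocation.

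- Section 7.2.4 gives the aim: "Subjects will be equally randomized across all sites to ensure equal and equivalent active device and" sham groups. It leaves the tool open, either one supplied by the sponsor or the EDC module.
- Section 10.2 gives the size: "A total of 102 subjects are required for this study, with 51 in each group". The synopsis repeats it.
- Section 10.3 gives the method: "A simple randomization scheme is used to allocate subjects into the treatment group or the sham group". It adds that "Site staff will be blinded to the randomization list".

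No section mentions blocks, strata, minimisation or a cap on arm size.

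On analysis, section 10.5 says of the active arm's change from baseline that "The primary efficacy endpoint will be analyzed using a paired, one-sided t-test", and of the sham comparison at Week 8 that "The secondary endpoint will be analyzed using a two sample one-sided t-test". Section 4 adds a post-treatment comparison: "Comparing SSS 1 month post-treatment (12 weeks) between the active device group and sham group". Laterality is recorded at baseline (7.2.3) and appears in section 4 only as an exploratory subgroup: "Change in SSS at 4 and 8 weeks in a unilateral subgroup compared to a bilateral subgroup". Exploratory endpoints are handled descriptively (10.5).

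**The concern.** Read literally, simple randomisation assigns each subject independently with probability one half. It cannot ensure equal arms or comparable groups, so the plan claims a property that its named method lacks. Whoever sets up the randomisation tool cannot tell from the text which scheme to build.

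Two things are at stake. First, the primary test uses the active arm alone, so chance in the allocation feeds directly into the primary sample size. Second, the sham comparison makes no use of laterality, in allocation or in analysis, although it is the one factor on which section 5.2 reports a marked difference in pilot response.

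**Working it through.** **The plan's own sample size.** Inputs from 10.2: difference 0.4, SD 0.7, one-sided alpha 0.05, power 0.80, attrition 25%.

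n per arm = 2 × (1.645 + 0.842)² × 0.7² / 0.4² = 37.9, so 38 completers. Then 38 / 0.75 = 50.7, so 51 per arm and 102 in total. This matches 10.2.

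**Arm sizes under simple randomisation.** The active arm is X ~ Binomial(102, 0.5), with SD 5.05 and 95% range 41 to 61.

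- P(X = 51) = 0.079
- P(arms differ by 10 or more) = 2 × P(X ≤ 46) = 0.373
- P(arms differ by 20 or more) = 2 × P(X ≤ 41) = 0.059

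**Active completers.** Take the completion rate as 38/51 = 0.745 (25.5% random dropout).

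| Allocation | Distribution of active completers | 95% range | P(31 or fewer) |
|---|---|---|---|
| Simple | Binomial(102, 0.5 × 0.745) | 29 to 48 | 0.090 |
| Fixed 51 | Binomial(51, 0.745) | 32 to 44 | 0.022 |

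**Primary paired test.** One-sided, alpha 0.05, improvement 0.4, noncentral t. Section 10.2 does not say which SD of change was used for this test, so 0.7 is an assumption.

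| Active completers | SD 0.6 | SD 0.7 | SD 0.8 |
|---|---|---|---|
| 38 | 0.992 | 0.965 | 0.916 |
| 35 | 0.987 | 0.952 | 0.895 |
| 33 | 0.982 | 0.941 | 0.878 |
| 31 | 0.976 | 0.928 | 0.859 |

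The stated 0.94 is not reproduced exactly: at 38 completers and SD 0.7, power is 0.965 one-sided and 0.929 two-sided. It still serves as the plan's own benchmark.

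**Sham comparison.** Two-sample, one-sided t-test, SD 0.7: power is 0.795 at 38:38, 0.791 at 34:42 and 0.783 at 31:45.

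**Average over the allocation and dropout distributions.**

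| Test | Fixed 51:51 | Simple | Loss |
|---|---|---|---|
| Primary | 0.963 | 0.961 | 0.3 points (0.9632 − 0.9605) |
| Sham comparison | 0.793 | 0.789 | 0.4 points (0.7926 − 0.7890) |

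Simulated one-sided type I error of the two-sample t-test under simple randomisation was 0.049 to 0.050.

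**Laterality.** The documents do not give the bilateral share. If bilateral change in the pilot was zero, the overall and unilateral means imply 0.59/0.9 = 0.66 unilateral at 4 weeks and 0.79/1.2 = 0.66 at 12 weeks, so about one third bilateral. One half is used as an alternative. The simulations take 102 randomised, 25.5% dropout, total SD 0.7 in each arm, and a laterality contrast under the active device only.

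| Bilateral share | Contrast | Unadjusted power | Adjusted power |
|---|---|---|---|
| One third | 0.9 | 0.79 | 0.82 to 0.83 |
| One half | 0.9 | 0.79 | 0.82 |
| One third | 0.45 | 0.789 | 0.797 |
| One half | 0.45 | 0.791 | 0.795 |

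Type I error at one third bilateral was 0.050 unadjusted and 0.052 adjusted.

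Bilateral share differs between arms by more than 15 points in 11% of trials at randomisation and 17% among completers (14% and 20% at one half). In that 17%, the mean absolute shift in the treatment difference is about 0.09 SSS points (0.05 at half the contrast). The standard error is 0.7 × √(2/38) = 0.16.

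**Stratified blocks** (sizes 4 and 6, for illustration). The arms differed by at most 6 and were exactly 51:51 in about 55% of trials. Adjusted power was 0.83.

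**The case against.** The strongest reply is that this comes down to one verb. The sentence in 7.2.4 can be read as stating an aim, and the list mentioned in 10.3 may be a fixed 51/51 list, in which case the arm-size figures fall away. That stands: the documents do not settle it, and the figures are conditional on the literal reading.

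It is also fair that section 10.4 analyses completers, so exact equality would be lost in any case. With a fixed 51:51 and 25.5% random dropout, completer arms are equal in only 9% of trials and differ by 5 or more in 31%. The 7.9% therefore shows that the wording is wrong; it does not measure harm. The active completer count varies even with a fixed 51, and simple randomisation only widens the range.

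On laterality, the evidence is a pilot of 13 subjects that section 5.2 says was not powered for the contrast, and the contrast was measured at 4 weeks rather than 8. The gain in power is therefore conditional.

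A reader might infer that the trial is biased or underpowered, or that chance laterality imbalance undermines the sham comparison. The documents support none of these. Simple randomisation is valid, the average loss is under half a point, and variation due to laterality is already contained in the planning SD of 0.7. Nor is stratification needed for validity.

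**Conclusion.** The inconsistency is real and of low severity. Sections 7.2.4 and 10.2 claim what the method in 10.3, taken literally, gives only in expectation. Type I error and unbiasedness are unaffected.

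The main practical effect is on the primary test: a roughly fourfold higher chance (9% against 2%) that the active arm ends with 31 or fewer completers. Even there, power is 0.928, about one point below the stated 0.94. This rests on independent 1:1 allocation, random dropout of 25.5% and an assumed SD of change of 0.7; at SD 0.8 the figure at 31 completers is 0.859.

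Laterality is a separate and optional source of precision, worth about three points of Week 8 power if the whole 0.9-point contrast is real under the active device, and about one point or less at half that. A larger gain would require a similar contrast under sham, for which the documents offer no data.

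**What to change.** Name one method, in the same words, in 7.2.4 and 10.3. Either option resolves the point.

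1. A restricted central 1:1 scheme: a fixed 51/51 list, or permuted blocks of varying, undisclosed size. If a fixed list was always intended, say so.
2. Simple randomisation, with the assurance of equality and equivalence removed from 7.2.4 and 51 per arm described in 10.2 as a target.

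Permuted blocks do not guarantee 51:51 either, so with blocks the same softening of 7.2.4 and 10.2 is needed.

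Separately, in 10.5, prespecify unilateral/bilateral status as a factor in the active-versus-sham comparison at Weeks 8 and 12.

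Stratifying the blocks by laterality is optional. It improves balance (a gap above 15 points among completers falls to about 1% of trials) but adds almost no power beyond the adjustment. If it is used, the adjusted analysis should accompany it, because the unadjusted t-test becomes slightly conservative (simulated type I error 0.041 to 0.044).

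The cost is text edits in 7.2.4, 10.2, 10.3 and 10.5, one degree of freedom for the laterality term, and no extra subjects. A restricted scheme also needs set-up in the randomisation tool before the first subject is randomised. Blocks add slight predictability, limited by undisclosed varying sizes and by the site blinding already planned.

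If subjects have already been randomised, document the method actually used and confine the change to the wording and the prespecified factor, settled before unblinding.
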